6.4. Unexpected Findings

MR scanning in this study is for research purposes only, and is not intended to diagnose or treat any disease or condition. Furthermore, study images shall not be reviewed or provided for diagnostic or any other purposes which may affect patient care. Study images are not being evaluated for specific clinical findings.

However, in the course of performing study procedures in any part of this study (Phase 1 or Phase 2), should the study staff observe unexpected findings, the Principal Investigator may choose to communicate such findings to the subject’s parent(s) or legally authorized representative(s) and/or other clinicians involved in the subjects routine clinical care. A report of an unexpected finding should clearly state that the study MRI scans have been reviewed only for technical purposes as required by the study and are not meant to supplement or replace any clinical MRI exam or MRI report as would be provided for standard of care exams. Further, it should be reported that the study scans were performed on an investigational device which is not yet approved for diagnostic imaging. Thus, any findings described cannot be guaranteed to be accurate or of clinical significance. The study Principal Investigator may note details of what is seen related to the unexpected finding to parent(s) or legally authorized representative(s) and/or, if necessary, to other clinician’s involved in the subject’s routine clinical care, but no diagnosis should be rendered based on study data. The study Principal Investigator may make recommendations for standard of care imaging follow-up, which, if necessary, will be conducted outside of this study. When an unexpected finding is reported, subjects in this study are then to be managed as patients with regard to standard of care in accordance with the site’s policies and procedures.

The Principal Investigator shall complete the study Investigator’s Report form regarding unexpected findings, or the noted absence thereof, for every study scan session. The PI may use this form to communicate findings to the responsible clinicians. The form should be stored in the study file, and a copy of the completed form may also be stored in any other location required or recommended by the General Medical Council record keeping guidelines.

6.4.1. Follow-up for Unexpected Findings

In Phase 1 of this study, if unexpected findings identified during this study result in referral for further MRI diagnostic evaluation or other medical care according to the standard of care at the investigational site, de-identified images and associated image data from the standard of care MRI may be observationally collected and provided to the Sponsor for engineering development and device optimization purposes. The occurrence of unexpected findings will be reported on the case report form (CRF). This data is being collected for exploratory engineering development and device optimization purposes, to learn more about performance characteristics and potential artefacts in Neonatal MRI scans. Images and associated image data will be provided at the discretion of the Principal Investigator, and may not be available for all patients with unexpected findings.

6.5. Withdrawal and Discontinuation Criteria

All subjects must be admitted for care in the NICU or other neonatal or infant care department or unit affiliated with the investigational site at the time of enrolment and scanning to be eligible to participate in this study. If a subject is discharged from clinical care at the investigational site prior to MR scanning, the subject will be withdrawn from the study.

The subject's medical care shall take precedence over any imaging or other procedures associated with the study.

If it is determined during the exam that the study imaging will in any way negatively impact required clinical care, the subject shall be immediately withdrawn from the study.

In the event the subject appears to be in pain or undue discomfort, if potentially destabilizing vital signs are observed by visual inspection or via monitoring equipment, or if the parent(s) or legally authorized representative requests to discontinue study procedures, the study procedures will be discontinued immediately and the subject will be removed from study, as determined necessary by the medically qualified staff at the investigational site. The subject shall be removed from the MR environment as soon as safely possible, and, if necessary, care will be provided to the subject to alleviate any discomfort according to the site's standard of care. Data collected up until the time of withdrawal may still be used and disclosed to the Sponsor for research purposes.

The subject's parent or legal guardian may withdraw him or her from study participation at any time, for any reason without consequence.

The study staff may withdraw a subject at any time for any reason.

The reasons for withdrawal and discontinuation for any subject shall be recorded. These will be reported to the Sponsor.

The EC/IRB should be notified per their notification of subject withdrawal policy.

There shall be no negative repercussions to the subject, parent(s) or legally authorized representative, or Study Staff for deciding end any study procedures.

6.6. Study Flowchart

Table 3– Flowchart detailing the data elements to be collected during each part of the study

Procedure/ Data Element	General Procedures (time interval)	Recruitment / Screening	Pre-Scan	MR Scanning	Post-Scan	Reader/ Evaluator Assessments
Quality Control Scan	Sponsor-set interval(s) ¹					
Specific Absorption Rate (SAR) Scans				X		
Running MR Scan Session Log	Daily verification			X		
MR Procedure Documents (Prepared by Sponsor)	Prior to enrolling first subject, thereafter at Sponsor-set regular interval ¹					
Qualitative Investigator Summary (Prepared by PI)	Within ~3 business days of completing MR Procedure document activities				X	
Inclusion/Exclusion		X				
Collect subject Information			X	X	X	
MR Safety (subject and any persons accompanying him or her into scan room)		X	X	X	X	
Application/Removal of Swaddling (if used)/Padding			X		X	
Transport			X		X	
Environmental conditions			X		X	
MR Procedure Document Identification (Version number)				X		
MR Scanning Information				X		
Software/Hardware components used				X (Phase 1 only) ²		
MR Scanner Technical Issues/Malfunctions				X		
Additional Sponsor-Requested Assessments			X	X	X	X(reader only)

Procedure/ Data Element	General Procedures (time interval)	Recruitment / Screening	Pre-Scan	MR Scanning	Post-Scan	Reader/ Evaluator Assessments
			(defined in MR Procedure Doc)	(defined in MR Procedure Doc)	(defined in MR Procedure Doc)	(defined in MR Procedure Doc)
MR Images and Data				X	X	X (access to)
Evaluable (Diagnostic)/Non-evaluable (Non-diagnostic) Assessment						X (reader and evaluators)
Image Quality Assessments						X (reader only)
Overall image quality (based on investigator's experience)						X (reader only)
Image contrast						X (reader only)
Presence of artefacts						X (reader only)
Signal to noise ratio (SNR)						X (reader only)
Tissue contrast						X (reader only)
Fat/water separation						X (reader only)
AEs/SAEs			X (From placement on swaddle, if used, or if not used from removal from clinical care environment to MR)	X	X (to removal from swaddle/padding and return to clinical care environment)	
MR System Errors/Issues				X		
MR Component/Accessories Errors/Issues			X	X	X	
Usability Assessments						
System Usability Scale (SUS)	Operator completes at end-of-scanning for					

Procedure/ Data Element	General Procedures (time interval)	Recruitment / Screening	Pre-Scan	MR Scanning	Post-Scan	Reader/ Evaluator Assessments
	each MR Procedure Docin Phase 1 and at end of Phase 2					
User Experience Scale (UXS)	Operator completes end-of-scanning for each MR Procedure Docin Phase 1 and at end of Phase 2					
Usability for Device Components					X	
Qualitative Investigator Summary	PI or designee completes for each Sponsor Investigator meeting in Phase 1					
End-of-Phase Summary Report	PI or designee completes at end of Phase 1 and Phase 2					

Note: X = to be conducted in indicated part of the study

1. Conducted at intervals set and determined by the study Sponsor. The PI ~~also~~ complete additional general quality scans that do not use human subjects (i.e. phantoms) any time during the study
2. For Phase 1 scanning only; In Phase 2 these components are ~~for~~ for all subjects by the applicable *MR Procedure Document* version

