3.4. Study Endpoints

3.4.1. Primary endpoints

For both Phase 1 and Phase 2, primary endpoints will be recorded as:

- Collection of MR images and associated data per quotas (Section 5.1.1 - Quotas by Anatomic Region)

- Performance will be determined by summary proportions of images determined to be of evaluable or non-evaluable diagnostic quality
- Safety will be determined by summary rates of adverse events

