6.3. Per-Subject Procedures

6.3.1. Pre-MR Scanning Activities

MR Pre-Screening

To verify that subjects with necessary medical equipment present can safely fit into the study device bore with normal airflow and without contact, subjects will be verified to be of acceptable size for study MR scanning using the Sponsor-provided sizing tool ("horseshoe" shaped ring) with necessary attached medical equipment prior to removal from the normal clinical care environment.

Note: The sizing tool is a study device that may only be used after written informed consent for participation has been attained.

The study staff will then ensure that the subject and any person(s) accompanying him or her into the MR environment satisfy all applicable site MR Safety Screening requirements.

If the subject is determined not be of appropriate size, not to meet MR Safety Screening policies at the site, or is discharged from clinical care at the investigational site prior to MR scanning, the subject will be withdrawn from the study.

Duration of Active Enrolment (for AE/SAE reporting purposes)

Subjects may be transported to the MR suite before or after removal from their incubator, crib, or other standard of care bedding.

Subjects will be considered actively enrolled (for AE/SAE reporting purposes) in the study on a per-subject basis from the time that the Sponsor-provided horseshoe-shaped sizing tool is used to measure subject size (the first study procedure of MR Pre-Screening). It is mandatory that the sizing ring is used for all subjects before other study procedures to ensure that the subject is of proper size for the MR bore.

Active enrolment will be considered to end on a per-subject basis upon the later of:

- a. The time that the subject is returned to his or her standard of care clinical environment and all Sponsor provided devices are removed from the subject, including Sponsor-provided swaddle, protective padding, and all other study devices.
- b. After active enrolment ends, images and data about any standard of care follow-up or other medical care resulting from unexpected findings may still be accessed observationally and collected by the Sponsor for research purposes.

Pre-Study Feed and Sleep Procedures

Per the applicable standard of care procedures required at the investigational site, each participating neonate or infant subject will be allowed adequate feed and sleep to ensure minimum disruption of care during MRI scanning, as follows:

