- a. The subject will be either breast or bottle fed by or in the presence of the parent/legal guardian.
- b. The subject will be placed in a position that is relaxed and comfortable, with the expectation that it will be reasonably possible for the subject to sleep through the MRI scan.

Swaddling Subjects and Use of Protective Padding

If used, unique identification number of the Sponsor-provided single-use disposable swaddle will be documented and noted on the swaddle log ([Appendix C – Example of Single-Use Disposable Swaddle Log](#)), and the following data will be collected during swaddling:

- Was a Sponsor-provided swaddle used (Y/N). If no, explain why not.
- Was other hospital-provided swaddling (e.g., blankets) used (Y/N); explain why
- Swaddle ID number
- Time of subject placement in the swaddle (on 24 hour clock)
- Swaddled shoulder circumference (in either swaddle or other padding)
- Shoulder-shoulder length before swaddling
- Description of when swaddling occurred (e.g., diapering, bathing, feeding or changing, etc.)
- Was backboard used (Y/N). If yes, explain why used

Subjects should be placed into the Sponsor-provided swaddles by trained study staff according to the instructions provided by the Sponsor. Subjects may be placed in the Sponsor-provided swaddles either immediately before transport to the MR suite or at an earlier time that will minimize subject discomfort, such as during routine feeding, bathing, or diapering. Efforts should be made to place subjects in the Sponsor-provided swaddles as close as possible to the time of MR scanning unless this presents a potential hazard or undue discomfort to subjects. If a swaddle is not used, the subject should be snugly placed in blankets provided by the investigational site, as such to prevent direct contact between the subject and the walls of the 3.0T Neonatal MRI investigational device (the bore) during scanning.

The site should follow the Sponsor's operator manual for specifications and application of padding to the subject prior to scanning, and padding provided by the Sponsor should be utilized for all subjects. At the discretion of the Principal Investigator or medically qualified delegate, the site may also apply necessary additional site-provide padding along with Sponsor-provided padding.

General Method for Recording Temperature

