Subject body temperature will be recorded at defined intervals before, during, and after scanning as detailed in the following sections. In the MR suite and during scanning, MR Safe In Vivo Expression monitors should be used to determine temperature and other vital signs.

Pre-Transport Subject Information

The following pre-scan session subject information will be recorded for all subjects:

- gender
- **age since birth**(days for subjects aged ≤ 30 days and months for subjects aged >30 days)
- gestational age (for subjects ≤ 30 days old)
- infant or neonate status (neonate = birth to ≤ 30 days; infant >30 days to <2 years)
- *Pre-transport temperature* body temperature just before leaving the incubator or crib, measured according to the standard clinical practice at the investigational site as follows:
 - temperature measurement value
 - device type (record standard of care device), and
 - anatomical area of measure (specific area of skin surface)
- head circumference
- weight on day of scan
- Additional Sponsor-Requested Assessments:
 - Blank areas will be included for these assessments (10 blank "Assessment Title" lines with associated 1-5 Likert scales) will be provided on the CRF to accommodate Sponsor-requested elements that may be specified for each *MR Procedure Document*. The investigator is responsible for being aware of any additional elements required by each *MR Procedure Document* version number. The investigational site(s) will be notified of any additional instructions for completing comments, and will be responsible for completing the comments field as instructed after appropriate training and instruction has been provided by the Sponsor.
- Investigator comments
 - The investigator is encouraged to make additional comments on any atypical or exceptional conditions of the subjects, including but not limited to pertinent medical history or known deformity.

Pre-Scan Subject Transport

The subject will be transported to the MR suite either before or after swaddling (whichever is less disruptive to the subject's care, in the opinion of the study staff) from his or her standard clinical care environment. The following parameters will be recorded about subject transfer to the MR scanning location:

- Transport mode into MR suite (subject moved by incubator/crib to MR suite or subject moved by transport cart/table)
- Time of removal from incubator/crib (on 24 hour clock)

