11. COMPLAINT HANDLING AND ADVERSE EVENT REPORTING

11.1. Foreseeable Adverse Events and Device Effects

MRI is generally considered safe for adults and babies because it does not involve exposure to ionizing radiation, such as x-rays. MRI of 4T or less is considered non-significant risk for infants and neonates, and population-specific risks are well described.^{26,30,31,32,33,34,35} The known risks typically associated with 3T MRI scans in this study are listed below and have been mitigated by the Sponsor to levels that are as low as reasonably practicable (ALARP), to levels equivalent or less than MRI using commercially released scanners:

Movement of Metal Objects Magnetic fields in MRI can cause internal or external ferrous metal (e.g. implants, umbilical cord clamps, oxygen tanks, infant security bands, scissors, paperclips, and pens) small enough to be innocuous to adults to move or become projectile, leading to minor injuries like cuts/bruises and, in rare cases, serious injury or death.

Thermal Effects Body temperature can change due to environmental cooling and/or MRI radiofrequency (RF) warming. Typical specific absorption rates (SAR) during study MRI scanning are not expected to cause injury. In rare cases, serious burns can occur that are typically related to metallic object presence or improper patient positioning.

Semi-permanent Cable/Device Removal Chest leads and other semi-permanent attached cables/devices can warm and electronics can function abnormally, potentially causing discomfort, injury, interruption of care, and, in rare cases, serious destabilization. Devices not known to be safe in the MRI environment may be removed or replaced when doing so does not detrimentally impact normal medical care, otherwise the subject will be withdrawn.

Peripheral Nerve Stimulation Transient skin sensations ('tingling') or peripheral nerve stimulation (PNS) is related to dB/dt and gradient rise time, and is expected to be rare in neonates and infants due to small skin surface area and conservative device thresholds. Subjecting infants to sudden, rapidly changing gradient magnetic fields during imaging can, induce circulating currents in conductive tissues of the body that typically are not painful and resolves spontaneously, though, in theory, discomfort or pain from PNS in infants is possible.²⁶

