11.3. Management of Adverse Event Reporting

Any adverse events will be recorded in the subjects study record and the Adverse Event Case Report Form. The following information should be obtained:

- Description of Event
- Date of onset and resolution
- Intensity (mild, moderate, severe)
 - **Mild:** Symptom(s) barely noticeable to the subject or does not make the subject uncomfortable. The AE does not influence performance or functioning. Prescription drugs are not ordinarily needed for relief of symptom(s).
 - **Moderate:** Symptom(s) of a sufficient severity to make the subject uncomfortable. Performance of daily activities is influenced. Treatment of symptom(s) may be needed.
 - **Severe** Symptom(s) of a sufficient severity to cause the subject severe discomfort. Treatment for symptom(s) may be given.
- Serious (yes/no)
- Relationship to device (unrelated, possibly related, probably related)
 - **Unrelated:** The adverse event is reasonably expected to be related to (or caused by) a concurrent illness, effect of another device/drug or other cause, and is unlikely related to the investigational product
 - **Possibly related:** The adverse event is reasonably expected to be related to the investigational product, and an alternative aetiology is equally or less likely compared to the potential relationship to investigational product
 - **Probably related:** There is a strong relationship to investigational product, or recurs on re-challenge, and another aetiology is unlikely, or there is no other reasonable medical explanation for the event.
- Treatment given and/or action taken (procedure stopped, withdrawn from study, no action)
- Anticipated (yes/no)

Adverse events that occur during a subject's active enrolment (as described in Section 6.3.1. - Pre-MR Scanning Activities: Duration of Active Enrolment) will be reported to the local EC/IRB per their policy and, if applicable, to regulatory agencies. Medical events that occur outside of

the active study during observational data collection, such as during standard of care follow-up conducted for any unexpected findings, will not be considered study adverse events.

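### Table 3 starts AE/SAE collection later than the reporting window in Section 6.3.1, on which Section 11.3 relies; the table cell is the likely outlier and should be aligned

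*Combined protocol and SAP*

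**What the plan says.** Three current parts of the protocol bear on when adverse event collection begins.

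- **Section 6.3.1, Duration of Active Enrolment**, is headed as applying to AE/SAE reporting. It counts a subject as actively enrolled "from the time that the Sponsor-provided horseshoe-shaped sizing tool is used to measure subject size (the first study procedure of MR Pre-Screening". The same section makes the ring mandatory before other study procedures and places the check before removal from the normal care environment.
- **Section 11.3** first asks, without a time limit, that any adverse event be entered in the study record and on the AE case report form. It then specifies which events go to the ethics committee and, where applicable, to regulators: those during "active enrolment (as described in Section 6.3.1. - Pre-MR Scanning Activities: Duration of Active Enrolment". It does not name the ring; it takes the start from Section 6.3.1.
- **Section 6.6, Table 3, AEs/SAEs row, Pre-Scan column**, marks collection "From placement on swaddle, if used, or if not used from removal from clinical care environment to MR".

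Section 3.4.1 states the endpoint that these data feed: "Safety will be determined by summary rates of adverse events".

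**The concern.** Table 3 is the protocol's schedule of data elements, so a site coordinator or form designer could reasonably work from it. Someone who did so would start AE collection at a later moment than someone working from Section 6.3.1. Both texts are current.

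The interval between the two starts is not empty. After the ring check, "The study staff will then ensure that the subject and any person(s) accompanying him or her into the MR environment satisfy" the site's MR safety screening requirements, so staff are still preparing the infant. Section 11.1 lists removal of cables and devices as a source of foreseeable adverse events: "Devices not known to be safe in the MRI environment may be removed or replaced". The protocol does not say when such removal happens, so it can, but need not, fall in this interval.

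The start rule also decides which infants have an AE window at all. Because AE rates are the primary safety endpoint, the rule for what counts should read the same wherever it appears.

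**Working it through.** No arithmetic applies, and the protocol gives no figure to reproduce. The check is to order the start events and compare the texts.

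1. **Order of events.** By Section 6.3.1, the ring check precedes all other study procedures, hence swaddling, and also precedes removal from the care environment. Both of Table 3's start events therefore come after the Section 6.3.1 start.

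2. **Swaddled infant.** Section 6.3.1 opens at the ring check and Table 3 at swaddling. Table 3 omits the time between them.

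3. **Infant not swaddled.** Table 3 opens at removal from care and omits the time from the ring check to removal.

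4. **Infant withdrawn in between.** Section 6.3.1 withdraws infants who prove to be the wrong size, fail MR safety screening or are discharged before scanning. If this happens before swaddling or removal, Table 3 never opens, although Section 6.3.1 already has.

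5. **Transport.** One passage of Section 6.3.1 says "The subject will be transported to the MR suite either before or after swaddling". For an infant swaddled on arrival, Table 3 would also omit transport. The swaddling passage in the same section points the other way: "Subjects may be placed in the Sponsor-provided swaddles either immediately before transport to the MR suite or at an earlier time". Transport is therefore omitted only if the first order is followed.

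6. **Which text is out of line.** Section 6.3.1 is the defining section, Section 11.3 cites it, and only the table cell differs. No clause says that narrative text overrides a table, so this is an inference.

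7. **What other sections still capture.** Section 2.5.5 makes the principal investigator responsible for promptly reporting device-related adverse events and product complaints, with no window. Section 11.4 requires all SAEs and UADEs to be reported, also with no window. The sizing ring is listed as a system accessory in Section 2.1.2, so harm attributed to the ring would be device-related. What remains exposed is mainly the non-serious event judged not device-related.

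8. **End of the window.** The two texts are close but not identical. Table 3's post-scan cell ends at removal from swaddle or padding and return to care. Section 6.3.1 requires return to care and removal of all Sponsor-provided devices, and Section 6.3.3 names the patient monitor among these.

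**The case against.** The strongest reply is that this is a stale flowchart cell with little consequence. Section 11.3 tells staff to record any adverse event, without a start time. Device-related events, SAEs and UADEs must be reported under Sections 2.5.5 and 11.4 whatever Table 3 says. Table 3's own row for component and accessory issues has an unrestricted pre-scan mark, so problems with the ring are collected. Section 6.5 requires the reason for every withdrawal to be recorded and reported to the Sponsor, so an infant who leaves after the ring check is not invisible. The study is single-arm and descriptive, tests no hypothesis (Section 3.1) and sets no AE threshold for success (Section 8.4).

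Most of this stands, and it narrows the point to the events identified in step 7 of the working. It does not remove the contradiction: Table 3 and Section 6.3.1 name different starts for the same row of data, and nothing in the protocol says which to follow. A recorded withdrawal reason is also not an adverse event record.

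A reader might infer that events before swaddling will be lost and that the reported AE rate will be too low. The documents do not support that. It would require the site or the AE case report form, which is not among the documents, to follow the table cell over Sections 6.3.1 and 11.3. A reader might also infer that the narrative sections formally govern. They are the better guide, but no passage says so.

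**Conclusion.** The inconsistency is real and sits in current text. Table 3 opens AE/SAE collection after the Section 6.3.1 reporting window in every case, and not at all for an infant withdrawn between the ring check and swaddling or removal. The table cell is the likely outlier.

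The size of any effect on summary AE rates cannot be estimated and may be zero. The documents give no length for the interval, no event rate within it, no rate of withdrawal after sizing and no denominator for the AE rates. Any effect depends on Table 3 being followed in practice.

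This should be corrected because it is an operating rule for the primary safety endpoint. It does not call the design or the analysis into question.

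**What to change.** - Change the Table 3 AEs/SAEs pre-scan cell to: from first use of the sizing ring (see Section 6.3.1). The word first matters because Section 6.3.1 also requires the ring immediately before scanning.
- Have the post-scan cell refer to the end of active enrolment in Section 6.3.1: return to the care environment with all Sponsor-provided devices removed.
- Check that the AE case report form instruction uses the same start and end.

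The cost is two table cells and one check of a form instruction. No procedure, data item, subject or analysis is added.
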